	
Extension Period (28 weeks) – HiSCR responders
 
Subjects from all cohorts who are HiSCR responders at Week 16 will receive IFX-1 at a dose of 800 mg q4w, starting at Week 20 through Week 40. If they have a loss of response (see Definitions of Terms) during the Extension Period, they will have an optional visit 2 weeks later. Subjects who then have a loss of response at the subsequent (planned) visit will be discontinued from the study and will not switch to the non-responder schedule.
 
Extension Period (28 weeks) – HiSCR non-responders
 
Subjects from all cohorts who are HiSCR non-responders at Week 16 will receive IMP during an Induction Phase (Weeks 18 and 19), followed by IFX-1 at a dose of 800 mg q2w during the Maintenance Phase.
 
Cohort 1:
 
 
• Induction Phase: infusion of IFX-1 800 mg at Weeks 18 (Days 127 and 130) and 19
 
• Maintenance Phase: IFX-1 800 mg at Week 20 and every other week through Week 40
 
 
Cohort 2:
 
 
• Induction Phase: infusion of IFX-1 800 mg at Week 18 (Day 127), placebo at Week 18 (Day 130), and IFX-1 800 mg at Week 19
 
• Maintenance Phase: IFX-1 800 mg at Week 20 and every other week through Week 40
 
 
Cohorts 3, 4, and 5:
 
 
• Induction Phase: infusion of IFX-1 800 mg at Week 18 (Day 127), and placebo at Week 18 (Day 130) and Week 19
 
• Maintenance Phase: IFX-1 800 mg at Week 20 and every other week through Week 40
 
 
Subjects who experience Worsening or Absence of Improvement (WOAI) (see Definitions of Terms) at 2 consecutive visits during the Maintenance Period of the Extension Period will be discontinued from the study.

Study duration	
The study duration for an individual subject will be up to 48 weeks and includes the following study periods:
 
 
• Screening Period: up to 18 days before first administration of IMP (Week -4 to Week -2 [Day -28 to Day -10])
 
• Main Period: starts with the first infusion of IMP on Week 0 (Day 1) and ends at Week 16 (Day 113), after administration of IMP
 
• Extension Period: starts after administration of IMP at Week 16 and ends at Week 44
 

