**Table 2 Dosing Schedule by Cohort in Main Period (Double-Blind)**

	Induction Phase				Maintenance Phase							
Visit	V2	V3	V4	V5	V6	V7	V8	V9	V10	V11	V12	
Week	0	0	1	2	4	6	8	10	12	14	16	
Day	1	4	8	15	29	43	57	71	85	99	113	
Cohort 1 (Placebo)	P	P	P	P	P	P	P	P	P	P	P	
Cohort 2 (400 mg q4w)	400	400	P	P	400	P	400	P	400	P	400	
	Cumulative IFX-1 dose: 2000 mg											
Cohort 3 (800 mg q4w)	800	800	800	P	800	P	800	P	800	P	800	
	Cumulative IFX-1 dose: 4800 mg											
Cohort 4 (800 mg q2w)	800	800	800	800	800	800	800	800	800	800	800	
	Cumulative IFX-1 dose: 8000 mg											
Cohort 5 (1200 mg q2w)	800	800	800	1200	1200	1200	1200	1200	1200	1200	1200	
	Cumulative IFX-1 dose: 10,800 mg											

HiSCR = Hidradenitis Suppurativa Clinical Response; IMP = investigational medicinal product; P = infusion of placebo; q2w = every two weeks; q4w = every four weeks; V = scheduled visit for all subjects.

400, 800, or 1200 = infusion of 400, 800, or 1200 mg IFX-1.

NOTE: cumulative doses refer to the amount of IFX-1 (doses marked in bold) received at the time the primary efficacy endpoint is assessed at Week 16 (percentage of subjects with a response, as measured by HiSCR [Section 8.2.2.2]), before administration of IMP at Week 16.

---

**Extension Period:** at Week 20 (Day 141) (HiSCR responders) or at Week 18 (Day 127) (HiSCR non-responders), subjects will receive the first administration of IMP during the 28-week Extension Period, as shown in [Table 3](#).

Subjects who are HiSCR responders at Week 16 (response on the basis of HiSCR is defined in Section [8.2.2.2](#)) will receive IFX-1 at a dose of 800 mg q4w during the Extension Period, starting at Week 20 through Week 40 (Day 141 to Day 281). If they have a loss of response (see [Definitions of Terms](#)) during the Extension Period, they will have an optional visit 2 weeks later. Subjects who still have a loss of response at the subsequent (planned) visit will be discontinued from the study and will not switch to the non-responder schedule.

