### 7.3 Extension Period (28 Weeks)

Subjects from all cohorts who are HiSCR responders at Week 16 (response on the basis of HiSCR is defined in Section [8.2.2.2](#)) will receive IFX-1 at a dose of 800 mg q4w, starting at Week 20 through Week 40. Subjects who have a loss of response (see [Definitions of Terms](#)) during the Extension Period will have an optional visit 2 weeks later. Subjects who still have a loss of response at the optional visit will be discontinued from the study and will not switch to the non-responder schedule.

Subjects from all cohorts who are HiSCR non-responders at Week 16 (response on the basis of HiSCR is defined in Section [8.2.2.2](#)) will receive IMP during an Induction Phase (Weeks 18 and 19), followed by IFX-1 at a dose of 800 mg q2w during the Maintenance Phase from Week 20 through Week 40 (see also [Table 3](#)). Subjects who experience WOI (see [Definitions of Terms](#)) at 2 consecutive visits during the Extension Period will be discontinued from the study.

Subjects who have been discontinued will have a Post-Treatment FUV 3 months after discontinuation or when another HS therapy has been started.

Due to the distinction between subjects according to their HiSCR responder status at Week 16, separate Schedules of Assessments are available for HiSCR responders ([Schedule of Assessments - Extension Period \(HiSCR Responders at Week 16\)](#)) and HiSCR non-responders ([Schedule of Assessments - Extension Period \(HiSCR Non-Responders at Week 16\)](#)).

#### HiSCR Responders at Week 16

Before administration of IMP, the following assessments and procedures will be performed at the visits to the study site, as indicated:

- Urine pregnancy test, required for all women of childbearing potential (*Weeks 20, 24, 28, 32, 36, 40*), only applicable for France
- Blood sample for analysis of safety laboratory parameters (*Weeks 20 [Denmark and France], 24 [France only], 28 [France only], 32, 36 [France only], 40 [France only]*)
- Physical examination (*Week 32*)
- ECG (*Week 32*)
- Vital signs (*Weeks 20, 24, 28, 32, 36, 40, and at optional visits*)
- HS clinical parameters (*Weeks 20, 24, 28, 32, 36, 40, and at optional visits*)
- Erythema assessment (*Weeks 20, 24, 28, 32, 36, 40, and at optional visits*)
- Continue documentation of patient-reported outcomes:

- Patient's Global Assessment of Skin Pain (NRS) (*daily in e-diary throughout Extension Period*)
- Analgesic therapy (*daily in e-diary throughout Extension Period*)

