- Patient's Assessment of Drainage (*daily in e-diary throughout Extension Period*)
- DLQI (*Week 32*)
- HADS (*Week 32*)
- SF-36v2 (*Week 32*)
- EQ-5D-5L (*Week 32*)
- Citrate plasma sample for analysis of:
  - IFX-1 (*Weeks 20, 24, 28, 32, 36, 40*)
- Plasma sample for analysis of:
  - C3a (*Week 32*)
  - C5a (*Weeks 24, 32*)
- Serum and plasma biomarker sample (*Week 32, not applicable for Denmark*)
- Serum sample for analysis of:
  - CH50 (*Week 32*)
  - CRP (*Weeks 20 [France only], 24 [France only], 28 [France only], 32, 36 [France only], 40 [France only]*)
  - ADAs (*Weeks 24, 32*)
- Photographic documentation of affected areas (*Weeks 24, 32*)
- Documentation of AEs (*Weeks 20, 24, 28, 32, 36, 40, and at optional visits*)
- Documentation of concomitant therapy (*Weeks 20, 24, 28, 32, 36, 40, and at optional visits*)

After the assessments and procedures listed above have been completed:

- Administration of IMP according to the dosing schedule shown in [Table 3](#) (*Weeks 20, 24, 28, 32, 36, 40 for q4w dosing*)

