## 10.4 Endpoints

### 10.4.1 Efficacy Endpoints

The primary efficacy endpoint is the percentage of subjects with a response on the basis of the HiSCR (Section 8.2.2.2) determined at Week 16, before administration of IMP.

The secondary efficacy endpoints are:

- Percentage of subjects with a response on the basis of the HiSCR determined at Week 12, before administration of IMP

- 
- Number of subjects with flares analyzed in terms of  $\geq 25\%$  increase in AN count among subjects with a minimum increase of 2 in AN count relative to Day 1
  - Absolute values and absolute and relative change in mSS from Day 1 by time point
  - Absolute value and absolute and relative change in Patient's Global Assessment of Skin Pain (NRS) from Day 1 by time point
  - Percentage of subjects achieving, by time point:
    - At least a 30% reduction and at least 1 unit reduction from Day 1 among subjects with baseline NRS  $\geq 3$  in Patient's Global Assessment of Skin Pain (NRS30)
    - At least a 50% reduction and at least 2 units reduction from Day 1 among subjects with baseline NRS  $\geq 3$  in Patient's Global Assessment of Skin Pain (NRS50)
  - Absolute values and absolute and relative change in DLQI score from Day 1 by time point

Exploratory efficacy endpoints:

- Percentage of subjects with  $\geq 50\%$  reduction in AN count compared to Day 1 by time point
- Percentage of subjects with no increase in number of abscesses compared to Day 1 by time point
- Percentage of subjects with no increase in number of draining fistulas compared to Day 1 by time point
- Percentage of (partial) responders measured by HiSCR and HiSCR25 by time point
- Percentage of subjects with  $\geq 25\%$  relative and  $\geq 2$  absolute increase in counts, using the abscess count, the inflammatory nodule count, and the draining fistula count by time point
- Achievement of clear or minimal severity of HS-PGA among subjects with at least 2 grades of improvement (reduction) from Day 1 to each time point.

The endpoints that are evaluated by time point will be analyzed in a similar way during the Extension Period. Summary tables for the Extension Period will be grouped by HiSCR responders and non-responders.

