## **10.10 Handling of Missing Data**

Data imputation rules are defined for missing values for the primary efficacy endpoint of percentage of subjects with a response, as measured by HiSCR at Week 16. Subjects with missing baseline assessments (baseline assessments might be obtained at Screening or at Day 1 before first infusion of IMP) necessary for the calculation of the HiSCR at Week 16 will not be randomized (i.e., there shall be no missing baseline values for HiSCR). Missing values for assessments at Week 16 necessary for the calculation of HiSCR at Week 16 will be replaced by multiple imputation, as described in section [10.5.1](#).

All other missing data will not be replaced.

Sensitivity analyses will be conducted based on the PPS. Further sensitivity analyses (e.g., evaluating patients with missing HiSCR at Week 16 as non-responders) will be defined in the statistical analysis plan if deemed necessary.

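### Section 7.3 removes a responder for loss of response at the optional visit, while five other places use the next planned visit; the loss-of-response words and formula also differ at a tie

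*Combined protocol and SAP*

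**What the plan says.** Six places in the current text say when a Week 16 responder who loses response leaves the study. All six begin in the same way: loss of response is found, and an optional visit follows 2 weeks later. They then divide.

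- **Section 7.3:** "Subjects who still have a loss of response at the optional visit will be discontinued from the study".
- **Synopsis, Section 1.4.3 and Section 3.1:** "Subjects who then have a loss of response at the subsequent (planned) visit will be discontinued from the study".
- **Section 5.4.2 and Section 6.2.2:** "Subjects who still have a loss of response at the subsequent (planned) visit will be discontinued from the study".

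Optional and planned visits are distinct. The responder Schedule of Assessments gives optional visits their own column, and Section 7.3 lists them apart from the planned weeks. HS clinical parameters, and so the lesion counts, are assessed at both.

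Loss of response is defined in the Definition of Terms and again in Section 10.4.1. In both places the words say at least 50% of the AN improvement from baseline to Week 16 has been lost. The formula in both places requires AN to be strictly greater than the midpoint of the baseline and Week 16 counts.

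**The concern.** A site working from Section 7.3, which sets out the Extension Period procedures, can remove a subject whom a site working from Section 5.4.2 or 6.2.2 would keep. Section 6.2.2 lists the rule among the circumstances in which treatment must stop, so it is not advisory.

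The analysis consequence lies in the Extension Period. Section 10.4.1 says: "The endpoints that are evaluated by time point will be analyzed in a similar way during the Extension Period". Those tables are grouped by Week 16 responder status. Section 10.10 imputes only the primary endpoint and adds: "All other missing data will not be replaced". The section that a site follows therefore affects which responders contribute to later time points. Long-term efficacy and safety is a stated secondary objective.

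The inequality feeds both the stopping rule, which refers to the Definition of Terms, and the loss-of-response percentage in Section 10.4.1.

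**Working it through.** **1. The rules side by side.** Let t be the planned visit at which loss is first found. The optional visit is then at t+2 weeks and the next planned visit at t+4.

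| Loss at t+2 | Loss at t+4 | Section 7.3 | Synopsis, 1.4.3, 3.1 ('then') | 5.4.2, 6.2.2 ('still') |
|---|---|---|---|---|
| Yes | No | Removed at t+2 | Kept | Kept |
| No | Yes | Kept at t+4 | Removed at t+4 | Depends on reading |
| Yes | Yes | Removed at t+2 | Removed at t+4 | Removed at t+4 |

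Row 1 conflicts under any reading (example: loss at Weeks 24 and 26, none at Week 28). Row 2 conflicts with the 'then' wording (loss at Weeks 24 and 28, none at Week 26). The word 'still' can mean either that loss is present again or that it has persisted throughout.

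**2. Size per subject.** Inputs from Section 7.3 and Table 3:

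- 800 mg infusions at "Weeks 20, 24, 28, 32, 36, 40 for q4w dosing", so 6 in all.
- Planned lesion counts at those six visits plus Week 44, so 7 in all.
- Assessment comes before infusion: "Before administration of IMP, the following assessments and procedures will be performed at the visits to the study site, as indicated".

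Assumptions: first loss at a planned visit, removal by this rule only, no omitted infusions, and no infusion at a visit where the subject is removed. All loss/no-loss sequences over the planned visits and the optional visits 2 weeks after them were enumerated.

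Worked case, row 1 with t = 20:

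- Section 7.3 removes at Week 22, after 1 infusion and 1 planned lesion count.
- The planned-visit rule keeps the subject at Week 24. The earliest later removal is Week 32, after losses at Weeks 28 and 32. By then there are 3 infusions (Weeks 20, 24, 28) and 4 planned counts.
- If the subject stays to Week 44 there are 6 infusions and 7 counts.
- Differences: 3 − 1 = 2 to 6 − 1 = 5 infusions (at most 5 × 800 = 4000 mg), and 4 − 1 = 3 to 7 − 1 = 6 counts.

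| First loss at Week | 20 | 24 | 28 | 32 | 36 | 40 |
|---|---|---|---|---|---|---|
| Row 1: fewer infusions under 7.3 | 2–5 | 2–4 | 2–3 | 2 | 1 | 0 |
| Row 1: fewer planned lesion counts under 7.3 | 3–6 | 3–5 | 3–4 | 3 | 2 | 1 |
| Row 2 ('then'): more infusions under 7.3 | 1–5 | 1–4 | 1–3 | 1–2 | 1 | 0 |
| Row 3: difference in infusions | 0 | 0 | 0 | 0 | 0 | 0 |

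The row 1 ranges are the same whether 'then' or 'still' is used.

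If the infusion were given at the removal visit, the infusion differences become:

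- Row 1: 3–5, 3–4, 3, 2, 1, 0 fewer.
- Row 2: 0–4, 0–3, 0–2, 0–1, 0, 0 more.
- Row 3: 1, 1, 1, 1, 1, 0 fewer.

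**3. The inequality.** Write B for baseline AN and W for Week 16 AN. The words require (AN − W) ≥ ½(B − W), which rearranges to AN ≥ ½(B + W). The formula requires AN > ½(B + W). They differ only at AN = ½(B + W), which a whole-number count can reach whenever B + W is even. With B = 4 and W = 2 the midpoint is 3: the words trigger at AN 3, the formula at AN 4.

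Taking B ≥ 3 (inclusion criterion 7) and W ≤ B/2 (the AN part of HiSCR), a tie value exists in 16 of 32 pairs for B from 3 to 10, 59 of 117 for B up to 20, and 126 of 252 for B up to 30. That is about half of the possible pairs. It is not a share of patients, because the document gives no distribution of AN counts.

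**The case against.** The strongest reply is that the effect is narrow. Only responders whose status differs between the optional and the planned visit are treated differently, apart from timing, and their number is unknown. Both rules remove subjects for lost response, so later responder summaries are selected under either. This is true, and it limits the size of the point without settling which rule applies.

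Other objections stand in part:

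- Section 7.4 allows loss of response to be followed up at an unscheduled visit with lesion counts. If the first loss is found there, the 2-week and 4-week spacing need not hold. The figures above apply only to a first loss at a planned visit.
- The optional visit may not be held, and Section 7.3 then gives no test. This is a further gap in that rule.
- Removed subjects still have the Week 44 assessments at early discontinuation, and a Post-Treatment follow-up visit. The lesion-count differences are therefore counts at planned time points, not net losses of all data. For a first loss at Week 40, the one missing count is Week 44 itself, and the discontinuation visit carries the same assessments.
- Removal for another reason can reduce any difference to 0.
- The inequality matters only at an exact tie, and Section 10.1 leaves exact endpoint definitions to the statistical analysis plan. That plan can settle the reported percentage, but not the trigger that sites apply during the study.

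A five-to-one count of passages suggests an intention, but nothing in the protocol gives those sections precedence over Section 7.3.

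**Conclusion.** The concern holds as stated. Section 7.3 contradicts five other places on the visit that confirms loss of response, and at least one visit pattern gives opposite decisions under any reading. Under the stated assumptions the per-subject effect runs from 0 to 5 infusions, the maximum needing a first loss at Week 20 and, for the undisputed pattern, a retained subject who stays to Week 44. The number of subjects affected cannot be estimated from the document.

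The visit conflict does not touch the Week 16 primary endpoint, the sample size, or a percentage of subjects who ever lost response, since the first loss is already counted. It does affect Extension Period disposition, exposure and the by-visit summaries of responders.

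The inequality is a smaller, separate error. It can move the stopping trigger at an exact tie, and it changes the reported percentage only for subjects who reach the midpoint and never exceed it. Both should be corrected.

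**What to change.** Reconcile Section 7.3 with the Synopsis and Sections 1.4.3, 3.1, 5.4.2 and 6.2.2 so that all six name the same confirmation visit. The choice belongs to the sponsor.

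- If it is the optional visit, state what applies when that visit is not held.
- If it is the planned visit, use one wording ('then' or 'still') throughout and say whether the optional-visit result counts.
- Use the same inequality in the words and the formula, in both the Definition of Terms and Section 10.4.1.

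The cost is wording in a protocol amendment, with whatever ethics and authority review Section 11.4 requires. The rewording itself adds no visits or data collection, although naming the optional visit as confirmatory would raise the question of whether it stays optional.

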### **HiSCR Non-Responders at Week 16**

Before administration of IMP, the following assessments and procedures will be performed at the visits to the study site, as indicated:

- Urine pregnancy test, required for all women of childbearing potential (*Weeks 20, 24, 28, 32, 36, 40*), only applicable for France
- Blood sample for analysis of safety laboratory parameters (*Weeks 20 [Denmark and France], 24 [France only], 28 [France only], 32, 36 [France only], 40 [France only]*)
- Physical examination (*Week 32*)
- ECG (*Week 32*)
- Vital signs (*Weeks 18 [Days 127 and 130], 19, 20, 22, 24, 26, 28, 30, 32, 34, 36, 38, 40*)
- HS clinical parameters (*Weeks 20, 22, 24, 26, 28, 30, 32, 34, 36, 38, 40*)
- Erythema assessment (*Weeks 20, 22, 24, 26, 28, 30, 32, 34, 36, 38, 40*)

- Continue documentation of patient-reported outcomes:
  - Patient's Global Assessment of Skin Pain (NRS) (*daily in e-diary throughout Extension Period*)
  - Analgesic therapy (*daily in e-diary throughout Extension Period*)
  - Patient's Assessment of Drainage (*daily in e-diary throughout Extension Period*)
  - DLQI (*Week 32*)
  - HADS (*Week 32*)
  - SF-36v2 (*Week 32*)
  - EQ-5D-5L (*Week 32*)
- Citrate plasma sample for analysis of:
  - IFX-1 (*Weeks 18 [Days 127 and 130], 19, 20, 22, 24, 26, 28, 30, 32, 34, 36, 38, 40*)
- Plasma sample for analysis of:
  - C3a (*Week 32*)
  - C5a (*Weeks 18 [Day 127], 24, 32*)
- Serum and plasma biomarker sample (*Week 32*), *not applicable for Denmark*
- Serum sample for analysis of:
  - CH50 (*Week 32*)
  - CRP (*Weeks 20 [France only], 24 [France only], 28 [France only], 32, 36 [France only], 40 [France only]*)
  - ADAs (*Weeks 18 [Day 127], 24, 32*)
- Photographic documentation of affected areas (*Weeks 18 [Day 127], 24, 32*)
- Documentation of AEs (*Weeks 18 [Days 127 and 130], 19, 20, 22, 24, 26, 28, 30, 32, 34, 36, 38, 40*)
- Documentation of concomitant therapy (*Weeks 18 [Days 127 and 130], 19, 20, 22, 24, 26, 28, 30, 32, 34, 36, 38, 40*)

After the assessments and procedures listed above have been completed:

- Administration of IMP according to the dosing schedule shown in [Table 3](#) (*Weeks 18 [Days 127 and 130], 19, 20, 22, 24, 26, 28, 30, 32, 34, 36, 38, 40*)

After administration of IMP:

- Citrate plasma sample for analysis of IFX-1, to be taken after end of IMP administration (+ 10 min) using a separate infusion line (*Week 18 [Day 130]*)

### **Follow-Up Visit at Week 44 (Safety Follow-Up)/3-Month Post-Treatment Follow-Up Visit**

The following assessments and procedures will be performed at the FUV to the study site at Week 44, as indicated:

- Blood sample for analysis of safety laboratory parameters
- Serum pregnancy test, required for all women of childbearing potential
- Physical examination

- 
- ECG
  - Vital signs
  - HS clinical parameters
  - Erythema assessment
  - Conclude documentation of patient-reported outcomes:
    - Patient's Global Assessment of Skin Pain (NRS) (*e-diary*)
    - Analgesic therapy (*e-diary*)
    - Patient's Assessment of Drainage (*e-diary*)
    - DLQI
    - HADS
    - SF-36v2
    - EQ-5D-5L
  - Citrate plasma sample for analysis of:
    - IFX-1
  - Plasma sample for analysis of:
    - C3a
    - C5a
  - Serum and plasma biomarker sample, *not applicable for Denmark*
  - Serum sample for analysis of:
    - CH50
    - CRP
    - ADAs
  - Photographic documentation of affected areas
  - Conclude documentation of AEs
  - Conclude documentation of concomitant therapy

For subjects who discontinue early, a Post-Treatment FUV will occur 3 months after the early discontinuation or when another HS therapy has been started, whichever occurs first. The subjects will be asked about any AEs and any concomitant therapy used since the previous visit to the study site.

## 7.4 Unscheduled Visits

Unscheduled visits (USVs) to the study site will be arranged as needed for subjects who require unscheduled follow-up assessments (e.g., due to an SAE, abnormal laboratory safety findings, loss of response, or WOAI).

The following assessments and procedures will be performed at USVs to the study site, as indicated:

- Vital signs
- HS clinical parameters

- 
- Erythema assessment
  - Continue documentation of patient-reported outcomes:
    - Patient's Global Assessment of Skin Pain (NRS) (*e-diary*)
    - Analgesic therapy (*e-diary*)
    - Patient's Assessment of Drainage (*e-diary*)
  - Documentation of AEs
  - Documentation of concomitant therapy

